7.3.4.2. Secondary Efficacy Endpoints Analyses

The % predicted FVC change from baseline will be analyzed using a similar model as the one described for the primary analysis.

The proportions of subjects who have an absolute decline of 10 percentage points or more in % predicted FVC or who die will be analyzed using logistic regression.

Treatment effect on time to death (all cause and respiratory-related) / hospitalization (all cause and respiratory-related), whichever occurs first, will be assessed using the log-rank test. Kaplan-Meier estimates will be derived for probability of death (all cause and respiratory-related) / hospitalization (all cause and respiratory-related) (whichever occurs first) over time and displayed graphically.

SGRQ total score and domains will be analyzed using descriptive statistics of actual values and changes from baseline at all time points. The proportion of SGRQ responders (defined as absolute change from baseline at all time points, in SGRQ total score \leq -4 points) will also be tabulated.

SGRQ responders and proportion of subjects with hospitalization will be described and tested for treatment differences using a Fisher's exact test.

More detail will be provided in the SAP.

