Subjects are not allowed to use non-evidenced based medication being used to treat IPF (i.e. warfarin; imatinib; endothelin inhibitors such as ambrisentan, bosentan, and macitentan; azathioprine; cyclophosphamide; cyclosporine A; methotrexate; sildenafil; prednisone at steady dose >10 mg/day or equivalent glucocorticoid dose) within 4 weeks before screening and during screening, or planned during the study. Subjects are also not allowed to use any other experimental oral IPF therapy within 12 weeks or 5-half-lives of the agent, whichever is longer, prior to screening, or to have participated in an investigational drug antibody / biologic study within 6 months prior to screening. This is necessary in order to avoid any confounding effects these drugs may have on the safety, tolerability, PK, [REDACTED] endpoints evaluated in the current study.

According to the analysis of the course of disease in placebo treated IPF subjects in clinical studies over 12 months by Nathan et al. [23] approximately 9.5% IPF subjects may experience a $\geq 10\%$ decline in % predicted FVC after 6 months compared with baseline. Nintedanib and pirfenidone have been shown to have a beneficial effect on the rate of decline in lung function. It is anticipated that a potential efficacious effect of GLPG1205 in IPF can be substantiated after this period of time and distinguished from individual courses of the disease in both populations – patients receiving nintedanib, pirfenidone, or neither nintedanib nor pirfenidone.

Pirfenidone is primarily metabolized in humans via CYP1A2 with minor contributions from other CYP isoenzymes. A clinical study assessing the effect of GLPG1205 on a CYP1A2 probe substrate (caffeine) demonstrated that there was no impact of GLPG1205 on the CYP1A2 probe substrate (no inhibition nor induction).

Pirfenidone is a weak P-glycoprotein (P-gp) inhibitor and is a weak CYP2C9, 2C19 or 1A2, 2D6, and 3A4 inhibitor. GLPG1205 is not an efflux substrate (P-gp, BCRP, multidrug resistance-associated protein 2 [MRP2]) and has multiple CYPs involved in its metabolism (3A4, 2C19). Consequently, the coadministration of GLPG1205 with pirfenidone should not lead to drug interactions however plasma levels of both GLPG1205 and pirfenidone will be measured and tolerability will be closely monitored.

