7.1. DETERMINATION OF SAMPLE SIZE

The aim of this proof-of-concept study is to show a trend in treatment difference for the primary endpoint (change from baseline in FVC over 26 weeks), therefore no formal sample size calculation was performed. In the following paragraph, the variability of the estimated treatment difference for the proposed sample size of 60 subjects is illustrated.

Consider 40 and 20 evaluable subjects in the GLPG1205 and placebo arm, respectively, and an aim of a 50:50 balanced study population being either on nintedanib/pirfenidone or neither. Further, assume for FVC change from baseline at Week 26 a common standard deviation of 200 mL, a true treatment difference of 50 mL in the population receiving nintedanib or pirfenidone and a true treatment difference of 80 mL in the population receiving neither nintedanib nor pirfenidone. Under these assumptions and taking into account 10% dropout, the probability to observe a treatment effect of more than 40 mL in the total study population is 67% and the probability to observe a treatment effect of more than 20 mL is 78%.

Approximately 60 subjects are planned to be randomized into the study.

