3.4.4. Stratification Factors

The analyses will be stratified by the type of IPF SOC medication taken at randomization: nintedanib or pirfenidone or neither. In all analyses, except if indicated otherwise, the stratum will be the SOC at randomization and will not change if the subject switches SOC during the study.

The 3 strata could differ in their safety profile, in addition, they might have different effects on the biomarker results (depending on the biomarker) and efficacy results. Therefore, for all analyses, 3 strata will be used (nintedanib, pirfenidone, neither), unless indicated otherwise.

The stratum reported in the case report form (CRF) will be used in the analyses. Any discrepancies in stratification reported in the interactive web response system (IWRS) versus CRF will be listed.

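### The analysis of 10-point decline in % predicted FVC or death names logistic regression with no readable sparse-data provision, yet only about 3 to 6 events are expected

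*Protocol*

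**What the plan says.** Protocol 7.3.4.2 gives this binary outcome one sentence: the proportions with an absolute decline of 10 percentage points "or more in % predicted FVC or who die will be analyzed using logistic regression". It names no covariates, no test, no penalised or exact option, and no rule for an arm without events. The section closes with "More detail will be provided in the SAP".

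The readable SAP does not mention this analysis. SAP 5.2.4 (Other Endpoints) is blacked out, as are parts of 5.5 (changes to planned analyses). On covariates, SAP 3.4.4 sets a default: "for all analyses, 3 strata will be used (nintedanib, pirfenidone, neither), unless indicated otherwise".

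The only event rate in the documents is in Protocol 2.3.2, where, from an analysis of placebo-treated subjects in other studies, "approximately 9.5% IPF subjects may experience a" decline of 10% or more in % predicted FVC after 6 months. Deaths are not part of that figure. On size, Protocol 7.1 says "Consider 40 and 20 evaluable subjects in the GLPG1205 and placebo arm, respectively", and its probabilities are given "taking into account 10% dropout".

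For two other binary outcomes, SGRQ response and hospitalization, Protocol 7.3.4.2 uses Fisher's exact test. SAP 5.3.1.7 uses Miettinen-Nurminen intervals for differences in adverse-event percentages.

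**The concern.** Unpenalised logistic regression has no finite treatment estimate when one arm has no events. With zero events on GLPG1205 the odds ratio is 0; with zero on placebo it is infinite. Either way the log odds ratio diverges, its Wald standard error is meaningless, and a profile-likelihood interval closes on one side only. If events are few, this is an ordinary outcome of the trial and should be planned for.

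Protocol 7.1 says the study aims to show a trend rather than to confirm an effect. An estimate with an interval is therefore the useful output of a supporting analysis such as this one, and it is the part at risk.

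**Working it through.** **The plan's own figures.** Protocol 7.1 assumes an SD of 200 mL and treatment differences of 50 and 80 mL in a 50:50 mix, so 65 mL overall. With 10% dropout, 40:20 becomes 36:18 and SE = 200 × √(1/36 + 1/18) = 57.7 mL. Then P(observed effect > 40 mL) = 1 − Φ((40 − 65)/57.7) = 66.7%, and P(> 20 mL) = 1 − Φ((20 − 65)/57.7) = 78.2%. The protocol states 67% and 78%, so its planning figures reproduce and 36:18 is the right reading of the dropout. It gives no event count or power for the decline-or-death outcome.

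**Inputs for this outcome.** Control rate p_c = 9.5% (Protocol 2.3.2); arm sizes n_t:n_c = 40:20 or 36:18 (Protocol 7.1); active rate p_t = RR × p_c, with RR of 1, 0.5 and 0.25 taken as assumptions.

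**Formulas.** Expected events = n_t p_t + n_c p_c. With A = (1 − p_t)^n_t for no events on GLPG1205 and B = (1 − p_c)^n_c for none on placebo, P(no finite log odds ratio) = A + B − AB.

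**Example, 40:20 with risk halved.** Events = 40 × 0.0475 + 20 × 0.095 = 3.8. A = 0.9525^40 = 0.143; B = 0.905^20 = 0.136; A + B − AB = 0.259.

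| Arms | RR | Expected events | A (drug) | B (placebo) | No finite estimate |
|---|---|---|---|---|---|
| 40:20 | 1 | 5.7 | 1.8% | 13.6% | 15% |
| 40:20 | 0.5 | 3.8 | 14.3% | 13.6% | 26% |
| 40:20 | 0.25 | 2.9 | 38.2% | 13.6% | 47% |
| 36:18 | 1 | 5.1 | 2.8% | 16.6% | 19% |
| 36:18 | 0.5 | 3.4 | 17.3% | 16.6% | 31% |
| 36:18 | 0.25 | 2.6 | 42.1% | 16.6% | 52% |

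**Sensitivity to the control rate** (40:20 / 36:18):

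- 5%: 44% / 49% with no effect; 59% / 64% with risk halved.
- 15%: 4% / 6% with no effect; 8% / 11% with risk halved.

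**Which RR fits the planned effect?** Assume a predicted FVC of 3.5 L and a 26-week placebo decline of 80 mL (neither is in the documents). Ten points is then 350 mL. With SD 200 mL, p_c = Φ((80 − 350)/200) = 8.9%, and with the 65 mL effect p_t = Φ((15 − 350)/200) = 4.7%, an RR of about 0.5. Placebo declines of 60-120 mL give control rates of 7-12.5% and a failure probability of 12-38% at 40:20. If predicted FVC is allowed to range over 3.0-4.0 L, the failure probability runs from 3% to 65%.

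**Adding stratum.** In simulation at 40:20 and 9.5%, the treatment estimate fails about as often as without stratum: 15%, 26% and 46% for RR 1, 0.5 and 0.25.

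**Tests.** Exact enumeration at 2% versus 15% (an assumed strong effect), two-sided 5%, for 36:18 / 40:20: Wald rejects in 12% / 16%, Fisher in 37% / 42%, and ordinary likelihood-ratio and score tests in 49% / 52%. With 9.5% in both arms, the likelihood-ratio test rejects in 7.2% / 7.4% and the score test in 3.8% / 3.9%.

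**The case against.** The strongest reply is that logistic regression is not tied to the Wald test. A reader might infer that the stated method loses power when the drug works well. The documents do not support that: Protocol 7.3.4.2 names no test, and the likelihood-ratio and score tests of an unpenalised model survive a single empty arm. In the example above they reject more often than Fisher, and the score test stays below its nominal level under no effect. This part of the reply stands.

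A reader might also infer that the failure belongs mainly to an effective drug. With no effect it comes almost wholly from zero placebo events, and with risk halved the two arms contribute about equally. Failure near one half needs risk cut to about one quarter, which is more than the planned FVC effect suggests.

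Stratum terms can look like a larger problem, because some coefficient becomes infinite in 40-68% of simulated trials at a 9.5% control rate. That count includes nuisance stratum coefficients, and an infinite one of those does not make the treatment odds ratio infinite.

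The 9.5% is uncertain in both directions. Deaths and the required prior progression (inclusion criterion 5.1b) would raise the rate, while background antifibrotics would lower it. Protocol 2.3.2 also does not say whether its 10% decline is absolute or relative.

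Finally, the redacted SAP text may already hold a sparse-data method, so it cannot be said that the plan as a whole lacks one. None of this restores a finite estimate or a two-sided interval under the method that can be read.

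**Conclusion.** The point holds as a limited one. On the protocol's own rate and arm sizes, the readable method yields no finite treatment odds ratio in roughly one trial in six with no effect and more than one in four with risk halved. The size depends on the 9.5% rate applying here and on the assumed risk ratios; at a 15% control rate it is about one in ten or less in those two cases. The failure concerns the point estimate, the two-sided interval and any Wald test. It does not extend to all testing.

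Severity is minor. The study is described as exploratory (Protocol 7.3.2), the outcome is not in the secondary lists of Protocol 4.1.2 or SAP 2.2.2, and nothing readable makes a decision depend on it.

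**What to change.** In Protocol 7.3.4.2 and the matching SAP text, specify Firth-penalised logistic regression with treatment and SOC stratum, and a profile penalised-likelihood test and confidence interval. State the number of stratum levels (three by the SAP 3.4.4 default) and add no further covariates. Also report the risk difference with the Miettinen-Nurminen interval already used in SAP 5.3.1.7. If the redacted text already does this, confirming it is enough.

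For illustration, take no events among 40 subjects on GLPG1205 and 3 among 20 on placebo. Without stratum, the Firth estimate equals adding one half to each cell. The odds become 0.5 to 40.5, or about 0.012, on GLPG1205 and 3.5 to 17.5, or 0.2, on placebo. Their ratio is about 0.06, with penalised likelihood-ratio p = 0.02 (Fisher p = 0.033). The unpenalised odds ratio is 0, with no lower limit on the log scale.

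The cost is one sentence of text and one option in the SAS code, with no new data. The odds ratio is shrunk slightly. Power stays low: even Fisher's test has only about 9% at 40:20 with risk halved from 9.5%. At 2% versus 15% the Firth test rejects about as often as Fisher's (37-42%), less than the unpenalised likelihood-ratio or score test. The change makes the result reportable rather than decisive.

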7.3.5. Analyses of Safety Data

All safety analyses will be performed using the full analysis set (Section 7.2.3). All safety data collected on or after the first dose of IMP administration up to the last follow-up visit after the last dose of IMP, unless specified otherwise, will be displayed in listings of individual data and/or summarized by treatment group according to the IMP received. Clinical safety will be addressed by assessing AEs, laboratory assessments, physical examinations, vital signs, and 12-lead ECGs.

7.3.5.1. Extent of Exposure

A subject's extent of exposure to IMP will be generated from the IMP administration page of the CRF. Exposure data will be summarized by treatment group. Duration of exposure to IMP will be expressed as the number of weeks between the first and last dose of IMP, inclusive, regardless of temporary interruptions in IMP administration and summarized by treatment group.

7.3.5.2. Adverse Events

Clinical and laboratory AEs will be coded using the latest version of the Medical Dictionary for Regulatory Activities. System organ class), High Level Group Term, High-Level Term, Preferred Term, and Lower-Level Term will be attached to the clinical database.

The following AEs will be considered as treatment-emergent adverse events (TEAEs):

Any AE (or worsening of any AE) with an onset date on or after the IMP start date and no later than 30 days after last dose of IMP.

Summaries (number and percentage of subjects) of TEAEs by System Organ Class and Preferred Term will be provided by treatment group. TEAEs will also be summarized by causal relationship to IMP or standard of care and by severity. In addition, TEAEs leading to premature discontinuation or dose reduction of IMP will be summarized. All AEs, non-treatment-emergent AEs, SAEs, AEs leading to hospitalization, AEs leading to death, deaths, AEs leading to discontinuation of IMP/standard of care and AEs leading to temporary stop or dose-reduction of IMP/standard of care will be listed.

7.3.5.3. Clinical Laboratory Evaluations

Laboratory assessments and their changes from baseline will be analyzed descriptively by treatment group.

7.3.6. Pharmacokinetic Analyses

Observed GLPG1205, nintedanib and pirfenidone plasma concentrations will be analyzed using a population PK approach to characterize the PK profile of GLPG1205 in IPF subjects and determine the covariates which might influence the PK in this population.

[REDACTED]

[REDACTED]

[REDACTED]

[REDACTED]

[REDACTED]

[REDACTED]

[REDACTED]

[REDACTED]

8. DATA MONITORING

8.1. INDEPENDENT DATA MONITORING COMMITTEE

To enhance the safety of the subjects, an IDMC consisting of independent recognized international experts will be convened to regularly review the accumulating unblinded safety data for the clinical study. The IDMC will provide a recommendation to the sponsor on clinical study continuation, suggestions for clinical study adaptation(s) or early termination. Ultimately, the final decision, to continue, adapt or early terminate the study, remains with the sponsor. The specific responsibilities, composition, meeting formats and details of output provided for the meetings of the IDMC are outlined in detail in the IDMC Charter.

8.2. CLINICAL ENDPOINT ADJUDICATION

Clinical endpoint adjudication will be performed by an experienced chest physician (and a back-up) and governed by a Charter which will be set up to perform, on a regular basis, a blinded adjudication of all cause and respiratory-related death and of all cause and respiratory-related hospitalization during the clinical study. The adjudication of these events will be performed in a blinded fashion for the purpose of data analysis (to enhance the integrity of the study data), and not for monitoring of subject safety. This objective data adjudication will reduce variation in outcome reporting and observer bias.

9. SAFETY REPORTING

9.1. DEFINITIONS OF ADVERSE EVENTS, AND SERIOUS ADVERSE EVENTS

9.1.1. Adverse Events

An AE is any untoward medical occurrence, new or worsening of preexisting one, in clinical study subject administered a medicinal product and which does not necessarily have to have a causal relationship with this treatment.

An AE can therefore be any unfavorable and unintended sign (for example, an abnormal laboratory finding), symptom, or disease temporally associated with the use of a medicinal product, whether or not considered related. AEs may also include pre- or posttreatment complications that occur as a result of CSP-specified procedures, worsening of the targeted disease, overdose, drug abuse/misuse reports, or occupational exposure. Preexisting events

that increase in severity or change in nature during or as a consequence of participation in the clinical study will also be considered AEs.

9.1.2. Serious Adverse Events

An SAE is defined as an AE that, results in the following:

- Death.
- Life-threatening (Note: The term ‘life-threatening’ in the definition of ‘serious’ refers to an event in which the subject was at risk of death at the time of the event; it does not refer to an event that hypothetically might have caused death if it were more severe.).
- In-subject hospitalization or prolongation of existing hospitalization.
- Persistent or significant disability/incapacity.
- A congenital anomaly/birth defect.
- Medically significant (medical and scientific judgment should be exercised in deciding whether other situations should be considered serious such as important medical events that might not be immediately life-threatening or result in death or hospitalization but might jeopardize the subject or might require intervention to prevent one of the other outcomes listed in the definition above).

9.1.3. Unlisted (Unexpected) Adverse Event/Reference Safety Information

An AE is considered unlisted if the nature or intensity is not consistent with the applicable product reference safety information. For an IMP, the expectedness of an AE will be determined by whether or not it is listed in the reference safety information part of the IB.

9.1.4. Adverse Events of Special Interest

Not applicable.

9.1.5. Clinical Laboratory Abnormalities and Other Abnormal Assessments as Adverse Events or Serious Adverse Events

Laboratory abnormalities without clinical significance based on the investigator’s judgement, are not considered AEs or SAEs. However, laboratory abnormalities (e.g. clinical chemistry, hematology and urinalysis) or other abnormal (clinical study specific) assessments (e.g. ECG, radiography, vital signs) that require medical or surgical intervention, are associated with signs and/or symptoms, lead to IMP interruption, modification, or discontinuation must be recorded as an AE or SAE if they meet the definition as described in Sections 9.1.1 and 9.1.2, respectively. If the laboratory abnormality is part of a syndrome, the syndrome or diagnosis is to be reported (e.g. anemia instead of decreased hemoglobin).

9.2. ASSESSMENT OF ADVERSE EVENTS AND SERIOUS ADVERSE EVENTS

The investigator is responsible for assessing AEs and SAEs for causality and severity. This is the basis for the sponsor’s final review and confirmation of accuracy and completeness of event information and causality assessments.

9.2.1. Assessment of Causality

The investigator is responsible for assessing the causal relationship to IMP(s) administration or study procedures (e.g. invasive procedures such as venipuncture) based on her/his clinical judgment. The following decision choice will be used by the investigator to describe the causality assessment between the reported event or laboratory test abnormality and the IMP.

- **Unrelated:**
Time relationship to drug intake is improbable. Related to other etiologies such as concomitant medications or subject's clinical state.
- **Unlikely:**
Time relationship to drug intake is improbable (but not impossible). Concomitant disease or other drugs provide plausible explanations.
- **Possible:**
Time relationship to drug intake is reasonable. Event or laboratory test abnormality, could also be explained by disease or other drugs. Information on IMP withdrawal may be lacking or unclear.
- **Probable:**
Time relationship to drug intake is reasonable. Unlikely to be attributed to concurrent disease or other drugs. Response to withdrawal is clinically reasonable and rechallenge not required.
- **Certain:**
Time relationship to drug intake is plausible. Cannot be explained by concomitant disease or other drugs. Response to withdrawal is plausible (pharmacologically, pathologically). Event definitive pharmacologically or phenomenologically (i.e. an objective and specific medical disorder or a recognized pharmacological phenomenon). Rechallenge satisfactory, if ethical and necessary.

It should be emphasized that ineffective treatment (worsening of the disease by the IMP) should not be considered as causally related in the context of AE reporting.

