2.2.4. Clinical Safety

Administration of single (up to 800 mg) and multiple (up to 100 mg q.d. for 14 days) oral doses of GLPG1205 in healthy male subjects can be considered well tolerated. No deaths, serious adverse events (SAEs) or treatment-emergent adverse events (TEAEs) leading to study drug discontinuation were reported. The most frequently reported treatment-related TEAEs were headache and gastrointestinal disorders like nausea and all TEAEs were rated at most moderate in intensity. None of the treatment-emergent abnormalities in laboratory, electrocardiogram (ECG) and vital signs parameters or physical examination abnormalities were considered clinically significant by the investigator.

Multiple dosing with GLPG1205 200 mg q.d. (first-in-human study - multiple ascending dose [MAD] part) did not show an acceptable safety profile with three subjects discontinuing the study drug due to headache after dosing with GLPG1205. Two subjects in the GLPG1205 200 mg q.d. group showed abnormally high laboratory values for hematocrit, hemoglobin and in red blood cell count, which were considered clinically significant by the investigator. This resulted in 100 mg q.d. being considered as the maximum tolerated dose after multiple dosing, which may be used in future clinical studies with GLPG1205.

Administration of a single GLPG1205 100 mg dose in fasted or fed state and co-administration of multiple doses of GLPG1205 100 mg with a single dose of a cocktail of CYP2C9, CYP2C19 and CYP1A2 substrates was considered well tolerated. Age or administration of a GLPG1205 loading dose (250 mg) did not affect the safety profile of GLPG1205.

In a Phase II study in subjects with ulcerative colitis, 63 subjects were dosed with 100 mg GLPG1205 q.d. or placebo for up to 12 weeks. No deaths were observed. Three subjects in the GLPG1205 group presented with treatment-related SAEs: worsening of ulcerative colitis (2 subjects) and macular rash (1), which led to study discontinuation. In addition, 5 subjects reported SAEs which were not considered treatment-related by the investigator, including worsening of colitis ulcerative (1 subject), anemia (1), worsening of colitis ulcerative and anemia (1), head injury (1) and tendon rupture (1).

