9.3.2. Serious Adverse Events

Subjects experiencing an SAE or an emergency situation will be examined by a physician as soon as possible. The subject will remain under observation as long as medically indicated. Appropriate laboratory tests will be performed until all parameters return to normal or are otherwise explained or stable.

Any SAEs that occur after the post treatment follow-up visit but within 30 days of the last dose of IMP(s), regardless of causality, should also be reported. Investigators are not obligated to actively seek SAEs after the CSP-defined follow up period, however, if the investigator learns of any SAEs that occur after clinical study participation has concluded and the event is deemed relevant to the use of IMP(s), he/she should promptly document and report the event to the sponsor at any time by using the SAE form.

All SAEs, whether or not deemed drug-related, must be recorded in the CRF and on the SAE form. The investigator must report each SAE immediately, and under no circumstances should this exceed 24 hours following the knowledge of the SAE, as is indicated on Page 2 under “Emergency Contact Information”.

The SAE form should at least contain identifiers of the subject and the reporter, SAE term and statement of relatedness to the IMP, and at a later stage if not yet available within 24 hours, the form needs to be completed with a clearly written narrative describing signs, symptoms, and treatment of the event, diagnostic procedures, as well as any relevant laboratory data and any sequelae.

Follow-up and outcomes should be reported and documented in the source documents for all subjects that experience an SAE. It is important that the information provided on the SAE form matches the information recorded on the CRF for the same event. In case an AE is ongoing at the time of the last follow-up visit, only the SAE form is to be updated, not the CRF.

Copies of additional laboratory tests, consultation reports, post mortem reports, hospital case reports, autopsy reports, and other documents should be sent when requested and available. Only subject identifiers should appear on the copies, and all names and initials should be blackened and rendered illegible. Follow-up reports relative to the subject’s subsequent course must be submitted until the event has subsided or, in case of permanent impairment, until the condition stabilizes.

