5.3.1.4. Treatment Relatedness

Following the guideline ICH-E3 Structure and Content of Clinical Study Reports (Step 4 Version), the originally reported relatedness to study drug of an AE will be dichotomized as follows:

- *Not study drug related*: all non-missing weaker levels of relatedness than ‘possibly drug related’.
- *Study drug related*: ‘possibly drug related’ and all stronger levels of relatedness (this class also includes any missing drug relatedness, as a worst-case consideration).

Only this dichotomized relatedness will be used in tables and can apply to different study drugs when relatedness has been collected separately per study drug; relatedness as originally reported will only be listed.

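### Protocol 9.2.1 merges lack of efficacy with worsening caused by the drug, so a site that follows it literally keeps suspected drug-caused IPF worsening out of the related-TEAE summaries

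*Protocol*

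**What the plan says.** Protocol 9.2.1 asks the investigator to rate each AE by clinical judgement on five levels: *Unrelated*, *Unlikely*, *Possible*, *Probable*, *Certain*. *Possible* needs a reasonable time relationship and says of the cause: "Event or laboratory test abnormality, could also be explained by disease or other drugs". The section then closes with an emphasised instruction that "ineffective treatment (worsening of the disease by the IMP) should not be considered as causally related in the context of AE reporting".

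The surrounding text:

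- **AE definition (Protocol 9.1.1).** Disease worsening is among the examples of an AE: "AEs may also include pre- or posttreatment complications that occur as a result of CSP-specified procedures, worsening of the targeted disease".
- **Sponsor review (Protocol 9.2).** The investigator's rating is the basis for the sponsor's "final review and confirmation of accuracy and completeness of event information and causality assessments".
- **SAE reporting (Protocol 9.3.2 and 9.4).** "All SAEs, whether or not deemed drug-related, must be recorded in the CRF and on the SAE form". SUSARs are notified under the regulations in force.
- **Analysis (SAP 5.3.1.4).** The rating is cut into two classes, with *Possible* and above counted as related. A missing rating also counts as related. "Only this dichotomized relatedness will be used in tables"; the rating as reported appears only in listings.
- **Outputs (Protocol 7.3.5.2, SAP 5.3.1.7).** TEAEs are summarized by causal relationship. The AE summary table has a line for TEAEs related to GLPG1205/placebo with a between-arm difference and 95% CI, and separate tables show related TEAEs by system organ class and preferred term.

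**The concern.** Lack of efficacy means that the disease takes its expected course despite treatment. Harm means that the drug speeds up or triggers deterioration. The first is rightly kept out of causality. The second is what a causality rating is meant to catch, and the bracket describes it in plain terms by naming the IMP as the cause of the worsening.

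In IPF the two are hardest to separate where it matters most, in respiratory deterioration and acute exacerbation. Protocol 9.1.4 defines no adverse events of special interest, so no such category picks these events out. If sites apply the bracket as written, a low count of related respiratory events could reflect the instruction rather than the drug, and that count could not be read as reassurance.

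**Working it through.** No figure in the plan bears on this point, so the check is a trace of one event through the documents, followed by the size of one subject in the affected table.

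**1. The event.** A subject's IPF worsens soon after starting IMP. The timing is plausible, the disease could also explain it, and the investigator suspects the drug.

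**2. Is it captured?** Yes. Protocol 9.1.1 makes it an AE, and an SAE if it meets a seriousness criterion.

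**3. How is it rated, and where does it go?**

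| Text applied | Rating | SAP 5.3.1.4 class | In related-TEAE outputs? |
|---|---|---|---|
| Five-level scale alone | *Possible* or higher | Related | Yes |
| Closing sentence, read literally | *Unrelated* or *Unlikely* | Not related | No |
| Closing sentence, read as lack of efficacy only | *Possible* or higher, since this is not mere inefficacy | Related | Yes |

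Two readings of the same section give opposite classifications. Choosing *Unlikely* instead of *Unrelated* does not help, because both fall below the SAP's cut. Nor does the SAP's worst-case rule for missing ratings, because here a rating has been given.

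**4. Where does the event remain on the literal reading?** In the all-TEAE, serious, fatal and severity outputs by arm (SAP 5.3.1.7); in blinded adjudication and the log-rank analysis if it led to death or hospitalization (Protocol 8.2, SAP 5.2.3.1); in FVC, the primary endpoint; and in the IDMC's unblinded review of safety and pulmonary function (SAP 4.1). One narrow exception: the SAP footnote to 5.3.1.1 counts a changed relationship as a worsening. A pre-treatment AE whose only change on treatment would have been an upgraded relationship could therefore also miss TEAE status.

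**5. What happens to expedited reporting?** SAEs in the study, and within 30 days of the last dose, go to the sponsor whatever their rating (Protocol 9.3.2). The sponsor then reviews causality, starting from the investigator's rating (Protocol 9.2). The starting point can be biased, but the review still takes place. For SAEs learned of after participation ends, reporting depends on whether they are deemed relevant to the IMP, so the investigator's causal view counts for more there.

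**6. Size of one subject.** Protocol 7.1 plans 40 subjects on GLPG1205 and 20 on placebo. The documents give no rate for suspected drug-caused worsening, so the number affected, k, is an assumption:

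- GLPG1205: k × 1/40 = k × 2.5 percentage points, so k = 1, 2, 4 gives 2.5, 5.0, 10.0 points.
- Placebo: one subject is 1/20 = 5.0 points.

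These are upper limits for the summary line, since a subject with another related TEAE stays in it. The study is blinded, so the instruction acts on both arms and the net shift in the difference can go either way.

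**The case against.** **The sentence is about inefficacy.** Its subject is ineffective treatment, its verb is advisory, and the section rests causality on clinical judgement. Many investigators would take it to mean only that failure to improve is not a drug reaction. This stands: a reader might infer that every such event must be coded *Unrelated*, and the text does not say so. But the benign reading requires the site to set aside the words in the bracket, and an instruction on causality should not depend on that.

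**Expedited reporting is protected.** A reader might infer that these events drop out of SUSAR assessment. The documents do not support this: SAEs in the study are reported regardless of causality, the sponsor reviews the rating, and regulations govern notification. What remains is possible bias, because that review builds on the investigator's rating.

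**A placebo-controlled trial does not need relatedness to detect harm.** The by-arm TEAE tables, adjudicated events, FVC and IDMC review compare arms directly. This stands, and it is the main reason the point is not graver. These outputs keep the event, but none of them restores the causality judgement. Interim AE outputs are also presented blinded (SAP 4.2), so the interim related-TEAE table could not have given an arm comparison in any case.

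**The earlier colitis study proves little about size.** Protocol 2.2.4 reports: "Three subjects in the GLPG1205 group presented with treatment-related SAEs: worsening of ulcerative colitis (2 subjects"), and macular rash in the third. A reader might infer that a known share of related SAEs would have vanished under this instruction. That does not follow. The same section lists two further subjects, arm not stated, whose SAEs included worsening colitis and were judged unrelated. That study's causality instruction is not in the documents, nor is the reason for each rating. It shows only that disease worsening was rated both ways in a study of this compound.

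**Conclusion.** The wording defect is confirmed. The bracket equates lack of efficacy with drug-caused deterioration and, read literally, contradicts the *Possible* level in the same section. On that reading a suspected drug-caused worsening of IPF becomes not drug related under the SAP and leaves the related-TEAE summaries.

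The size is unknown, because the documents give neither an event rate nor evidence of how sites read the sentence. Each affected GLPG1205 subject is worth at most 2.5 percentage points in the related-TEAE line, assuming all 40 planned subjects are treated. Primary analysis, randomization, AE capture and IDMC review are unaffected, and SUSAR review may be biased but is not removed. This is a should-fix in safety attribution.

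**What to change.** Delete the bracket and replace the closing sentence of Protocol 9.2.1 with wording such as: *Lack of efficacy, or progression of IPF as expected, is not by itself evidence of a causal relationship. Any AE of disease worsening, including acute exacerbation (Appendix 2), is assessed on the same five-level scale as every other AE.*

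Send this to sites as a clarification. Then run a causality query on respiratory and IPF-worsening AEs already recorded:

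- Fix the list of terms in advance and apply it to all subjects without reference to arm.
- Use neutral wording that does not invite an upgrade.
- Keep investigators and the staff who raise the queries blinded.
- Retain the previous rating in the audit trail.
- Finish before unblinding, since relatedness is subjective and later changes would add a bias of their own.

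The cost is one protocol sentence, a site letter and a small query round. The count of related events may rise slightly. The SAP needs no change.
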